2.3.2. Secondary Hypotheses

1. The Test lens will be non-inferior to the Control 1 lens with respect to binocular low luminance high contrast visual acuity. A non-inferiority margin of 0.1 LogMAR will be used
2. The Test lens will be no different than the Control 1 with respect to low luminance low contrast threshold without glare.
3. The Test lens will be no different than Control 1 with respect to the percentage of roads signs correctly identified at night driving.
4. The Test lens will be no different to Control 1 with respect to the average distance to correctly identify a pre-determined road sign at night driving.
5. The Test lens will be no different than the Control 1 with respect to the percentage of hazards avoidance at night driving.
6. The Test lens will be no different than the Control 1 with respect to average pedestrian recognition distance at night driving.

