1.4.2. Secondary Hypotheses

- 1. The Test lens will be non-inferior to the Control 1 lens with respect to binocular low luminance high contrast visual acuity. A non-inferiority margin of 0.1 LogMAR will be used.
- 2. The Test lens will be no different than the Control 1 lens with respect to low luminance low contrast threshold without glare.
- 3. The Test lens will be no different than the Control 1 lens with respect to the percentage of road signs correctly identified at night driving.
- 4. The Test lens will be no different than the Control 1 lens with respect to average distance to correctly identify a pre-determined road sign at night driving.
- 5. The Test lens will be no different than the Control 1 lens with respect to the percentage of hazards avoided at night driving.
- 6. The Test lens will be no different than the Control 1 with respect to average pedestrian recognition distance at night driving.

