6.2. Secondary Analysis Methods

Binocular distance visual acuity (LogMAR)

Binocular low luminance high contrast distance visual acuity will be analyzed using a linear mixed model to test for the difference between Test and Control 1. Sequence of lens wear, period, lens type, first order carryover effect will be included in the model as fixed effects. An appropriate covariance structure will be chosen to model the residual errors between measurements within the same subject across periods. Covariance structures considered will be:

- Compound Symmetry (CS)
- Heterogeneous Compound Symmetry (CSH)
- Unstructured (UN)
- Ante-dependence (ANTE(1))

For ANTE(1) structure, subject will be included in the model as random effects. The covariance structure that returns the lowest AICC will be selected as the structure that best fit the data.

The null and alternative hypotheses for non-inferiority of Test lens relative to Control 1 are as follows:

$$H_0: \mu_T - \mu_C \ge 0.1 H_A: \mu_T - \mu_C < 0.1,$$

where $\mu_T - \mu_C$ is the mean difference between Test lens and Control 1 lens. Non-inferiority of the Test lens relative to the Control 1 lens will be concluded if the upper limit of the 95% confidence interval of the LSM difference between Test and Control 1 is less than 0.1.

Low luminance contrast threshold (%)

Low luminance contrast threshold will be analyzed using a generalized linear mixed model with a binomial distribution and the logit and the link function. Sequence, period, lens type, first order carry-over, contrast level and the interaction contrast level by lens type will be included as fixed effects and subject as random effect. An unstructured covariance matrix (UN) will be used to model the correlation between measurements from the same subject and period across contrast level. If convergence problems are encountered with the unstructured covariance matrix, a model with compound symmetry covariance matrix (CS) will be considered

The null and alternative hypotheses for no-difference between Test and Control 1 are as follows:

$$H_0: OR = 1 H_A: OR \neq 1,$$

where OR is the odds ratio of the number of correctly identified orientation of the Landolt C. No statistical difference between Test lens and Control 1 lens will be concluded if 1 falls within the 95% confidence interval of the LSM ratio, OR, of Test Over Control 1.

Sign Recognition and Hazard Avoidance (%)

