Proportion of correctly identified sings and proportion of hazard avoidance will be analyzed separately using a generalized linear mixed model with beta distribution and logit link function. Each model will include sequence, period, lens type, first order carry-over, driving time (day or night), and the 2-way interactions: lens*time, sequence*time, period*time and carry*time as fixed effect factors. An unstructured covariance matrix (UN) will be used to model the correlation between measurements from the same subject across periods. If convergence problems are encountered with the unstructured covariance matrix, a model with compound symmetry covariance matrix (CS) will be considered. Non-significant interactions at the 15% significance level will be excluded from the model. The interaction between lens type and driving time will be forced into the final model.

The null and alternative hypotheses for no-difference between Test and Control 1 are as follows:

$$\begin{array}{l} H_0: OR = 1 \\ H_A: OR \neq 1, \end{array}$$

where OR is the odds ratio of hazard avoidance at night driving time of Test over Control 1. No statistical difference between Test and Control 1 will be concluded if 1 falls within the 95% confidence interval of the odds ratio.

Pedestrian Distance Recognition and Road Sign Recognition

Pedestrian distance recognition and road sign recognition distance (or log-transformed distance) will be analyzed separately using a linear mixed model; sequence of lens wear, period, lens type, first order carry-over, driving time (day or night), and the 2-way interactions: lens*time, sequence*time, period*time and carry*time will be included in the model as fixed effects. Age will be included as fixed covariate when appropriate. An appropriate covariance structure will be

selected to model the correlation between measurements across periods within the same subject and driving time. Covariance structures that will be considered include:

- Compound Symmetry (CS)
- Heterogeneous Compound Symmetry (CSH)
- Unstructured (UN)
- Ante-dependence (ANTE(1))

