For ANTE(1) structure, subject and driving time nested within subject will be included in the model as random effects. For the remaining structures only subject will be included as random effect. The covariance structure that returns the lowest Akaike Information Criteria Corrected (AICC) will be selected as the structure that best fit the data¹². Heterogeneous residuals covariance structures (R-side) across driving time will be considered when appropriate. The log-likelihood ratio test will be used to test for the homogeneity between the residual covariance structures. The Kenward and Roger method will be used for the denominator degree of freedom. Non-significant interactions at the 15% significance level will be excluded from the model. The interaction between lens type and driving time will be forced into the final model.

Results from the final selected model will be reported as least-square mean (LSM) estimates with 95% confidence intervals.

The null and alternative hypotheses for non-inferiority of Test lens relative to Control 1 are as follows:

$$H_0: \mu_T - \mu_C = 0$$

$$H_A: \mu_T - \mu_C \neq 0,$$

where $\mu_T - \mu_C$ is the mean difference of distance recognition at night driving between Test and Control 1. No statistical difference between Test and Control 1 will be concluded if 0 falls within the 95% confidence interval of the LSM difference between Test and Control 1.

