7. OTHER ANALYSIS

Further comparisons between the test lens and the control lenses will be conducted using the same models described in the primary and secondary analysis sections 5.2 and 6.2. The following hypotheses will be tested:

- The Test lens will be non-inferior to at least one of the Control lenses (Control 1 or Control 2) lens with respect to overall daytime driving performance. A non-inferiority margin of -0.25 will be used.
- 2. The Test lens will be non-inferior to the Control 2 lens with respect to overall night driving performance. A non-inferiority margin of -0.25 will be used.

- 3. The Test lens will be non-inferior to the Control 2 lens with respect to binocular low luminance high contrast visual acuity. A non-inferiority margin of 0.1 LogMAR will be used.
- 4. The Test lens will be no different than the Control 2 lens with respect to low luminance low contrast threshold without glare.
- 5. The Test lens will be no different than the Control 2 lens with respect to the percentage of road signs correctly identified at night driving.
- 6. The Test lens will be no different than the Control 2 lens with respect to average distance to correctly identify a pre-determined road sign at night driving.
- 7. The Test lens will be no different than the Control 2 lens with respect to the percentage of hazards avoided at night driving.
- 8. The Test lens will be no different than the Control 2 with respect to average pedestrian recognition distance at night driving.

Multiple comparisons between the test lens and the control lenses with respect to driving performance (Hypotheses 1 and 2) will be adjusted to control for type I error using bonferroni's method. For the remaining hypotheses, the comparisons will be conducted with a two-sided type I error rate of 5%.

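### Five secondary hypotheses predict no difference between Test and Control 1, and their only decision rule counts a non-significant result as support, with no margin

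*SAP*

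**What the plan says.** The hypotheses are worded as predictions of no difference. SAP 1.4.2 has "The Test lens will be no different than the Control 1 with respect to average pedestrian recognition distance at night driving", and protocol 2.3.2 has "The Test lens will be no different than the Control 1 with respect to the percentage of hazards avoidance at night driving". Hypotheses 2 to 6 all take this form, and none carries a margin.

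SAP 6.2 gives the decision rules:

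- **Contrast threshold (hypothesis 2):** "No statistical difference between Test lens and Control 1 lens will be concluded if 1 falls within the 95% confidence interval".
- **Sign percentage and hazard avoidance (hypotheses 3 and 5):** "No statistical difference between Test and Control 1 will be concluded if 1 falls within the 95% confidence interval of the odds ratio". The text covers both endpoints, but the odds ratio is defined for one only: "where OR is the odds ratio of hazard avoidance at night driving time of Test over Control 1".
- **Sign distance and pedestrian distance (hypotheses 4 and 6):** "No statistical difference between Test and Control 1 will be concluded if 0 falls within the 95% confidence interval of the LSM difference". The hypothesis block above this rule is introduced with "The null and alternative hypotheses for non-inferiority of Test lens relative to Control 1 are as follows", although the null written below it is a difference of exactly zero.

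Protocol 14.6 carries the same rule for the same endpoints. Its contrast-threshold model is Poisson, so the null there is a ratio of mean counts equal to 1. It also has the same non-inferiority label over the distance hypotheses.

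Two other tests are built differently. The primary test (SAP 5.2) needs the lower 95% limit to lie above -0.25. The low-luminance acuity test (SAP 6.2) needs the upper 95% limit to lie below 0.1 logMAR.

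SAP section 7, hypotheses 4 to 8, repeats the wording against Control 2, for example "The Test lens will be no different than the Control 2 with respect to average pedestrian recognition distance at night driving". It refers back to the same models and gives no decision rule of its own for these hypotheses.

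**The concern.** A 95% interval that contains the null shows only that the data do not exclude zero difference. It does not show that a difference large enough to matter has been ruled out. When the hypothesis itself predicts no difference and non-rejection is the only criterion given, failing to find a difference becomes the favourable result. If any true difference exists, less information makes that result more likely. A margin rule works the other way, because less information makes the favourable conclusion harder to reach.

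At stake are reported statements of no difference on five vision and driving measures in a study sized for the primary endpoint only (SAP 1.5). Protocol section 1 says that residual light absorption by a photochromic lens at night could reduce the visibility of low-contrast objects such as pedestrians. Low-contrast hazards and pedestrian recognition are among the endpoints judged by this rule.

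**Working it through.** **The plan's own figures.** There are none for these endpoints: no SD, margin or power. The power table in SAP 1.5 (71%, 85%, 95%) concerns the primary composite and is not used here.

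**Inputs**

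- Two-sided 5% level, 95% CI: SAP 2.1 and 6.2.
- n = 24 completers from 28 enrolled: SAP 1.5. I also take n = 22 and n = 20 as modest shortfalls.
- True difference δ of 0 to 0.5, in units of the SD of the within-person Test minus Control 1 difference (paired SD). This range is my assumption.

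**Model.** I use a paired t comparison as a stand-in for the planned mixed models. It ignores period, sequence and carry-over terms. Three of the five endpoints use a generalized linear mixed model, so for those it is only a rough guide.

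**Formula.** Let t* be the 97.5% point of t with n - 1 degrees of freedom, and let λ = δ√n, with δ in paired SDs. Then

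P(95% CI contains 0) = F(t*; n - 1, λ) - F(-t*; n - 1, λ),

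where F is the noncentral t distribution function.

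**At n = 24.** t* = 2.069 on 23 df, so the CI half-width is 2.069/√24 = 0.42 paired SD.

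| True difference (paired SD) | λ = δ√24 | P(rule concludes no difference) |
|---|---|---|
| 0 | 0 | 95% |
| 0.1 | 0.49 | 92% |
| 0.2 | 0.98 | 84% |
| 0.3 | 1.47 | 71% |
| 0.5 | 2.45 | 35% |

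**Fewer subjects, true difference 0.5 SD.** At n = 22, λ = 0.5 × √22 = 2.35, giving 39%. At n = 20, λ = 0.5 × √20 = 2.24, giving 44%.

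**Noisier data, n = 24.** If the SD is 1.5 times larger, the same raw difference becomes 0.5/1.5 = 0.333 SD. Then λ = 1.63, giving 65%.

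**No true difference.** The probability is 95% at every n and every SD. The dependence on precision arises only when a difference exists.

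**Units.** If errors are independent with equal variance, one paired SD is √2 within-subject SDs. A difference of 0.5 within-subject SD is therefore 0.5/√2 = 0.354 paired SD, and the rule returns no difference 62% of the time at n = 24.

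**The case against.** Four points can be made for the plan.

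1. **The sentence is literally true.** The SAP says no statistical difference, which correctly describes a non-significant test. That stands as far as it goes. But the hypotheses predict no difference and nothing else is offered to judge them by, so in use the rule is their success criterion.

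2. **The composite covers most of this.** Sign percentage, sign distance, hazard avoidance and pedestrian distance are four of the six components of the primary score, which is tested at night against -0.25. So driving similarity does not rest on the criticised rule alone, and only contrast threshold lies wholly outside the composite. It does not establish similarity for each component, however. With equal weights and the other five unchanged, a loss of 1.0 Z in one component lowers the composite by 1/6 = 0.167, inside the margin. Reaching 0.25 takes 0.25 × 6 = 1.5 Z.

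3. **Imprecision will be visible.** Estimates with 95% intervals are planned for the distance endpoints, and the Appendix A code requests confidence limits for the others. This helps an attentive reader, but it leaves the written conclusion in place.

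4. **The sample is protected.** The plan enrols 28 for 24, raises enrolment if dropout is high (SAP 1.5), and replaces subjects who discontinue (protocol 8.2). A reader might infer a dramatic swing from a much smaller trial: at n = 12 the 0.5 SD figure would be 65%. The arithmetic is right, but nothing in the documents suggests such a shortfall. The plausible change from lost subjects is 35% to about 39-44%.

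**Conclusion.** The concern holds. For secondary hypotheses 2 to 6, following the plan as written turns a non-significant result into support for similarity, with no margin, and no other section corrects this. The logical defect does not depend on the numbers.

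The size is illustrative. At 24 subjects, a true difference of 0.2, 0.3 or 0.5 paired SD would be reported as no difference with probability 84%, 71% or 35%. These figures rest on assumed SDs and a paired-t approximation. For very small differences, sample size hardly matters.

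A reader might infer that the trial's main conclusion is compromised, or that the sponsor plans a formal equivalence claim on these endpoints. The documents support neither. The primary and acuity tests use margins and are unaffected. SAP 1.2 links the study as a whole to a 510(k) submission, but no section assigns these five tests an equivalence role. This should be fixed, but it concerns secondary endpoints only.

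**What to change.** 1. **SAP 6.2, decision sentences.** Replace each of the three with: *The LSM difference (or odds ratio) of Test versus Control 1 will be reported with its 95% CI; a CI containing 0 (or 1) will not be interpreted as evidence of no difference.* Deleting them is not enough. Protocol 14.6 carries the same rule, and under SAP 1.1 the SAP overrides protocol section 14 only where the two differ.

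2. **SAP 6.2, hypothesis blocks.** Remove or relabel the null and alternative pairs for these endpoints to match. Correct the non-inferiority label over the zero-difference null, which also appears in protocol 14.6. Define the odds ratio for sign recognition as well as hazard avoidance.

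3. **Hypotheses.** Reword hypotheses 2 to 6 in SAP 1.4.2 as estimation aims. Do the same for hypotheses 4 to 8 in SAP section 7, together with its statement that they will be tested. Make the matching change in protocol 2.3.2 at the next amendment, since that section lies outside section 14 and the SAP does not supersede it.

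4. **If a similarity claim is wanted on any endpoint,** pre-specify a justified margin for that endpoint and require the CI to exclude it. Under the same paired-t assumptions and a true difference of zero, 24 subjects would exclude a one-sided margin of about 0.60 paired SD with 80% power, or about 0.69 paired SD in both directions.

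**Cost.** Items 1 to 3 are wording changes, one of which is a protocol amendment. Some endpoints will end as inconclusive. Item 4 costs more, because the documents supply no margins or SDs to start from.

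The Appendix A code needs repair whether or not this change is made. For example, the contrast-threshold ESTIMATE statement uses `lens`, which is not in its model; the distance model uses an undefined `time`; and `subjid` is missing from CLASS in the sign/hazard and distance models.

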7. OTHER ANALYSIS

Further comparisons between the test lens and the control lenses will be conducted using the same models described in the primary and secondary analysis sections 5.2 and 6.2. The following hypotheses will be tested:

- The Test lens will be non-inferior to at least one of the Control lenses (Control 1 or Control 2) lens with respect to overall daytime driving performance. A non-inferiority margin of -0.25 will be used.
- 2. The Test lens will be non-inferior to the Control 2 lens with respect to overall night driving performance. A non-inferiority margin of -0.25 will be used.

- 3. The Test lens will be non-inferior to the Control 2 lens with respect to binocular low luminance high contrast visual acuity. A non-inferiority margin of 0.1 LogMAR will be used.
- 4. The Test lens will be no different than the Control 2 lens with respect to low luminance low contrast threshold without glare.
- 5. The Test lens will be no different than the Control 2 lens with respect to the percentage of road signs correctly identified at night driving.
- 6. The Test lens will be no different than the Control 2 lens with respect to average distance to correctly identify a pre-determined road sign at night driving.
- 7. The Test lens will be no different than the Control 2 lens with respect to the percentage of hazards avoided at night driving.
- 8. The Test lens will be no different than the Control 2 with respect to average pedestrian recognition distance at night driving.

Multiple comparisons between the test lens and the control lenses with respect to driving performance (Hypotheses 1 and 2) will be adjusted to control for type I error using bonferroni's method. For the remaining hypotheses, the comparisons will be conducted with a two-sided type I error rate of 5%.

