CLASS tseqpg2 aperiod trta carry1a subjid parcat6 sexn ; MODEL aval/n= age sexn tseqpg2 aperiod trta|parcat6 carry1a / S DIST=BINOMIAL LINK=LOGIT; RANDOM INTERCEPT / SUBJECT=subjid; RANDOM parcat6 / RESIDUAL SUBJECT=aperiod(subjid) TYPE= covariance_matrix; ESTIMATE "Test vs Control1" lens -1 0 1, *secondary analysis; "Test vs Control2" lens 0 -1 1 / CL ILINK EXP; *other analysis;

RUN;

Where ads: Analysis data set n: number of targets subjid: subject identification sexn: Gender tseqpg2: Lens wear sequence (6 levels) aperiod: Study Period (3 levels) trta: Study lens type (Test, Control1, Control2) parcat6: Contrast level (4 levels) carry1a: First order carryover effect covariance_matrix: Compound Symmetry (CS) and Unstructured (UN)

Sign Recognition and Hazard Avoidance

PROC GLIMMIX DATA= ads;

CLASS driveseq asper trta carry1a parcat5 sexn; MODEL aval= age sexn driveseq asper|parcat5 trta|parcat5 carry1a / DDFM=KR2 S DIST=BETA LINK=LOGIT; RANDOM INTERCEPT / SUBJECT=subjid; RANDOM asper / RESIDUAL SUBJECT= parcat5 (subjid) TYPE=covariance_matrix; **Secondary analysis; ESTIMATE "Night: Test vs Control1" trta -1 0 1 trta*parcat5 0 -1 0 0 0 1 / CL ILINK EXP; **Other Analysis; ESTIMATE "Day: Test vs Control1" trta -1 0 1 trta*parcat5 -1 0 0 0 1 0, "Day: Test vs Control2" trta 0 -1 1 trta*parcat5 0 0 -1 0 1 0, "Night: Test vs Control2" trta 0 -1 1 trta*parcat5 0 0 0 -1 0 1 / ADJUST=bonferroni CL ILINK EXP ;

RUN;

Where ads: Analysis dataset subjid: subject identification sexn: Gender driveseq: Lens wear sequence (6 levels) asper: Study Period (3 levels) trta: Study lens type (Test, Control1, Control2) parcat5: Driving time (day or night) carry1a: First order carryover effect covariance matrix: Compound Symmetry (CS) and Unstructured (UN)

Pedestrian Distance Recognition and Road Sign Recognition

PROC GLIMMIX DATA= ads;

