CLASS driveseq asper trta carry1a parcat5 sexn; MODEL aval= age sexn driveseq asper|parcat5 trta|parcat5 carry1a / DDFM=KR2 S; RANDOM INTERCEPT / SUBJECT=subjid; RANDOM INTERCEPT / SUBJECT = parcat5(subjid); *only included if ANTE(1)is used; RANDOM asper / RESIDUAL SUBJECT=time (subjid) TYPE=covariance_matrix; LSMEANS trta*parcat5 /slicediff = parcat5 CL ; **Secondary analysis; ESTIMATE "Night: Test vs Control1" trta -1 01 trta*parcat5 0 -1 0 0 0 1 / CL ; **Other Analysis; ESTIMATE "Day: Test vs Control1" trta -1 01 trta*parcat5 -1 0 0 0 1 0, "Day: Test vs Control2" trta 0 -1 1 trta*parcat5 0 0 -1 0 1 0, "Night: Test vs Control2" trta 0 -1 1 trta*parcat5 0 0 0 -1 0 1 / ADJUST= bonferroni CL ;

RUN;

Where ads: Analysis dataset subjid: subject identification driveseq: Lens wear sequence (6 levels) asper: Study Period (3 levels) trta: Study lens type (Test, Control1, Control2) parcat5: Driving time (day or night) carry1a: First order carryover effect covariance_matrix: CS, CSH, UN and ANTE(1). The covariance structure that returns the lowest AICC will be selected as the structure that best fit the data.

REFERENCES

- 1. SAS Institute Inc: SAS® 9.4 Statements: Reference, Third Edition. Cary, NC: SAS Institute Inc; 2014.
- 2. SAS Institute Inc. 2015. SAS/STAT® 14.1 User's Guide. Cary, NC: SAS Institute Inc.
- 5. Wood, JM. (2002), Age and Visual Impairment Decrease Driving Performance as Measured on a Closed-Road Circuit. ProQuest Health and Medical Complete 44(3) 482
- Wood, JM., & Carberry TP. (2006), Bilateral cataract surgery and driving performance. Br. J. Ophthalmol 90, 1277-1280
- 8. Hickson L., et al. (2010), Hearing Impairment Affects Older People's Ability to Drive in the Presence of Distracters. The American Geriatrics Society 58: 1097-1103

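### SAP Appendix A requests a three-way Bonferroni adjustment for the night Test vs Control 2 contrasts of Hypotheses 5–8, which SAP section 7 tests at an unadjusted two-sided 5%

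*SAP*

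**What the plan says.** **Text.** SAP section 7 lists eight further hypotheses. Hypotheses 1 and 2 concern the overall driving score, and comparisons "with respect to driving performance (Hypotheses 1 and 2) will be adjusted to control for type I error using bonferroni's method". The next sentence covers the rest: "For the remaining hypotheses, the comparisons will be conducted with a two-sided type I error rate of 5" percent. Hypotheses 5–8 all compare Test with Control 2 at night:

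- Hypothesis 5: no difference "with respect to the percentage of road signs correctly identified at night driving".
- Hypothesis 6: no difference in "average distance to correctly identify a pre-determined road sign at night driving".
- Hypothesis 7: "The Test lens will be no different than the Control 2 lens with respect to the percentage of hazards avoided at night driving".
- Hypothesis 8: no difference in average pedestrian recognition distance.

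**Code.** In Appendix A, the Other Analysis statement for sign recognition and hazard avoidance has three rows: Day Test vs Control 1, Day Test vs Control 2, and Night Test vs Control 2. It ends with "ADJUST=bonferroni CL ILINK EXP". The block for pedestrian and sign recognition distance has the same three rows and ends with "ADJUST= bonferroni CL". The Test vs Control 2 rows for low-luminance acuity (Hypothesis 3) and contrast threshold (Hypothesis 4) carry no adjustment option.

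**Decision rule.** For these endpoints, section 6.2 concludes no statistical difference when the null value (odds ratio 1 or mean difference 0) lies inside the 95% interval. It is written for Test vs Control 1. Section 7 says the same models are reused for the further comparisons.

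**The concern.** The body and the appendix of the SAP set different error rates for the same four prespecified hypotheses. Appendix A is also inconsistent with itself, since two of the six remaining hypotheses are coded unadjusted and four adjusted.

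The direction matters. Bonferroni usually guards against too easy a favourable claim. Here the favourable claim is no difference, reached when the interval covers the null value, so widening the interval makes it easier to reach. If the choice between adjusted and unadjusted output is left open until the data are in, a borderline difference between Test and Control 2 can be reported either way, and each report can cite part of the SAP.

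**Working it through.** **Inputs**

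- Level for Hypotheses 3–8: 0.05, two-sided, unadjusted (SAP section 7).
- Contrasts under the Bonferroni option: m = 3 (rows of the ESTIMATE statement, Appendix A).
- Decision rule: null value inside the interval (SAP section 6.2). Applying it to Control 2 is an inference from the reuse of the same models.
- Degrees of freedom and true effects: not given in the documents, so assumed over a range.

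**Step 1. Text against code**

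| Hypotheses (section 7) | Endpoint | Text | Appendix A |
|---|---|---|---|
| 1, 2 | Driving score | Bonferroni | Bonferroni, 3 rows |
| 3 | Low-luminance acuity | 5%, unadjusted | No adjustment |
| 4 | Contrast threshold | 5%, unadjusted | No adjustment |
| 5, 7 | Sign percentage, hazards | 5%, unadjusted | Bonferroni, 3 rows |
| 6, 8 | Sign distance, pedestrian distance | 5%, unadjusted | Bonferroni, 3 rows |

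Text and code agree in the first three lines and conflict in the last two. For the driving score the three rows match the hypotheses: Hypothesis 1 needs both day contrasts and Hypothesis 2 needs the night one. For the other four endpoints section 7 states no daytime hypothesis, yet the two day rows count in the divisor.

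**Step 2. Per-contrast level.** The unadjusted output gives 0.05, which is section 7's figure. The adjusted output gives 0.05/m = 0.05/3 = 0.0167, a 98.3% interval, which is not.

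**Step 3. Interval width.** The ratio is the critical value at 0.0167 over that at 0.05, both two-sided.

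| Reference distribution | At 0.05 | At 0.0167 | Ratio |
|---|---|---|---|
| Normal | 1.960 | 2.394 | 1.22 |
| t, 110 df | 1.982 | 2.431 | 1.23 |
| t, 60 df | 2.000 | 2.463 | 1.23 |
| t, 40 df | 2.021 | 2.499 | 1.24 |
| t, 20 df | 2.086 | 2.613 | 1.25 |

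**Step 4. Which results change.** Adjusted p = min(1, 3 × raw p), so 0.02 becomes 0.06, 0.03 becomes 0.09 and 0.04 becomes 0.12. The conclusion differs for raw p between 0.0167 and 0.05 and for no other value.

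**Step 5. Chance of missing a true difference (normal approximation).** For power P at the 5% level, the standardised effect is 1.960 + z(P). Power at the adjusted level is Φ(1.960 + z(P) − 2.394).

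- P = 0.50: Φ(1.960 − 2.394) = Φ(−0.434) = 0.33
- P = 0.80: Φ(2.802 − 2.394) = Φ(0.408) = 0.66
- P = 0.90: Φ(3.242 − 2.394) = Φ(0.848) = 0.80

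Where the 5% test has 80% power, the chance of concluding no difference rises from 20% to 34%. Where it has 50% power, that chance rises from 50% to 67%. These figures apply only if the adjusted output is the one reported.

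**The case against.** The strongest reply is that the code does not force the adjusted result. In SAS, an adjustment option combined with confidence limits normally adds adjusted results beside the unadjusted ones. A reader might infer that following the code must reverse a borderline conclusion. The documents do not support that: the 95% interval that section 7 calls for would still be in the output. Sections 6.2 and 7 point to it, and section 11.2 has a second statistician check compliance with the SAP. This stands, and it makes the consequence conditional. It does not remove the gap. The SAP does not say which set of results governs, and its precedence statement (section 1.1) ranks it over protocol section 14 but does not rank its body against its appendix. Section 2.1, which speaks of an overall 5% error rate, could be cited for adjusting.

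A reader might also infer that the adjustment was chosen to favour the sponsor. Nothing supports that. The three-row block repeats the one for the driving score, where it belongs. The distance code also refers to a variable, time, that is not in its variable list, and both blocks omit the subject identifier from the CLASS list. Copying from a template is the plausible reading, and the point about direction concerns effect only.

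Two further replies are fair. The Day Test vs Control 2 row serves a stated aim, since protocol section 2.1.3 lists daytime performance against Control 2 among the other objectives. It still corresponds to no section 7 hypothesis for these endpoints. And inferring no difference from a non-significant test is a weakness in itself, which correcting the code leaves in place.

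**Conclusion.** The contradiction is real and concerns a decision threshold: 0.05 in section 7 against 0.0167 in the adjusted output that Appendix A requests for Hypotheses 5–8. If that output is reported, the interval is 22% wider on the normal scale, 23–24% with 40 to 110 df and 25% with 20 df. Raw p values between 0.0167 and 0.05 would then move from different to no different. This rests on two conditions that the documents do not settle: that the adjusted results are the ones reported, and that the section 6.2 rule carries over to Control 2. The power figures also rest on assumed effects.

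The scope is narrow. A reader might infer that the trial's main conclusions are exposed, but they are not. The primary and secondary night Test vs Control 1 contrasts in these code blocks sit in separate, unadjusted ESTIMATE statements, and the code for Hypotheses 3 and 4 already agrees with the text. This is a reconciliation worth making before the analysis is run. It does not threaten the primary result.

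**What to change.** In Appendix A, remove the Bonferroni option from the Other Analysis ESTIMATE statements in two blocks: sign recognition with hazard avoidance, and pedestrian with sign recognition distance. Hypotheses 5–8 then use the unadjusted 95% interval that section 7 states, in line with Hypotheses 3 and 4. Keep the option in the driving-score code. If adjustment was intended for Hypotheses 5–8, amend section 7 instead: say so, define the family (including whether the daytime contrasts belong to it), and state which interval decides.

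It would help to add one sentence to section 7 confirming that the section 6.2 rule applies to the Control 2 comparisons.

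The cost is two code edits in a SAP revision. Data collection, sample size and the primary and secondary analyses do not change. Relative to the adjusted output, the no-difference conclusions become somewhat harder to reach, as the section 7 text already provides.
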